6.4 SAFETY ANALYSIS

Safety will be assessed through evaluation of AEs, Laboratory data (hematology, chemistry, urinalysis), vital signs (blood pressure, heart rate, temperature, and respiratory rate), Physical examination, Neurological examination, 12-lead ECGs, Doppler ECHOs, Tanner Staging, BRIEF to measure cognition, and Columbia–Suicide Severity Rating Scale.

All safety analyses will be performed for the SAF population and will be reported for all subjects overall. Select analyses may be repeated by treatment group, for example, treatment-emergent adverse events initiating on or before Visit 2 (Week 2), Visit 3 (Month 1), and Visit 4 (Month 2).

6.4.1 Adverse Events

An AE is defined as any unfavorable and unintended sign (including an abnormal, clinically significant laboratory finding), symptom, or disease temporally associated with the use of a medicinal (investigational) product, whether or not considered related to the medicinal (investigational) product. The period of observation for adverse events extends from the time the subject gives informed consent until 15 days after the last dose of study drug or the last visit, whichever is later. For patients who continue into the open-label extension study, AEs from the core studies will be considered medical history unless there is an increase in the frequency or severity of the condition from the core study.

A TEAE is defined as any AE that based on start date information occurs after the first intake of study treatment. All other AEs occurring after enrollment and prior to the first administration of study treatment are defined as non-treatment emergent AEs (non-TEAEs).

AEs are categorized as related or not related to IMP. Per protocol, the following rule was used to assess causality of an AE to IMP:

- **Not Related:** Concomitant illness, accident or event with no reasonable association with study drug.
- **Related:** The event follows a reasonable temporal sequence from administration of study drug and is definitive pharmacologically; cannot be attributed to concurrent disease or other factors or medications. A clinically reasonable response should be observed if the study drug is withdrawn or dose reduced.

Any missing relationship/causality assessment will be considered as “related.”

The severity of AEs (whether non-serious or serious) will be assessed by the investigator as follows:

- Mild - A type of AE that is usually transient and may require only minimal treatment or therapeutic intervention. The event does not generally interfere with usual activities of daily living.
- Moderate - A type of AE that is usually alleviated with additional specific therapeutic intervention. The event interferes with usual activities of daily living, causing discomfort but poses no significant or permanent risk of harm to the research participant.
- Severe - A type of AE that interrupts usual activities of daily living, or significantly affects clinical status, or may require intensive therapeutic intervention.

Per the CDISC SDTM Severity Intensity Scale for Adverse Event Terminology, any missing severity will be imputed as “severe.”

The original terms used by the investigators in the eCRFs to identify AEs will be coded using the most recent version of the MedDRA implemented by the sponsor at the end of the study.

6.4.1.1 Overview of Adverse Events:

The number and percent of patients with at least one of the following events will be summarized in an overall summary table:

- TEAE
- Serious TEAE
- Related TEAE
- Related serious TEAE
- Severe TEAEs
- Adverse events of special interest
- Deaths

The percentage denominator for the calculation of percentage will be the number of subjects in the SAF population. The above summary will be provided for the OLE treatment period.

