6.2.7 Medical History

All ongoing conditions and relevant medical history from the past 5 years (including all major hospitalizations and surgeries) as well as the subject's current medical status and current medications will be carried over from the core study. AEs starting during the core study will be counted as medical history if they conclude prior to start of 1503. Ongoing AEs will be included as such in 1503.

Medical history will be summarized and sorted alphabetically, by primary System Organ Class and Preferred Term coded via the most recent version of Medical Dictionary for Regulatory Activities (MedDRA). The number and percentage of subjects will be displayed for each System Organ Class and Preferred Term within treatment group.

Medical history will be presented for the SAF population.

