At Least one Fatal TEAE	XX (XX.X%)	XX (XX.X%)	XX (XX.X%)	XX (XX.X%)	XX (XX.X%)	XX (XX.X%)	XX (XX.X%)
At Least one Related TEAE	XX (XX.X%)	XX (XX.X%)	XX (XX.X%)	XX (XX.X%)	XX (XX.X%)	XX (XX.X%)	XX (XX.X%)
At Least one Related Serious TEAE	XX (XX.X%)	XX (XX.X%)	XX (XX.X%)	XX (XX.X%)	XX (XX.X%)	XX (XX.X%)	XX (XX.X%)
At Least one TEAE Leading to Discontinuation of Study Treatment	XX (XX.X%)	XX (XX.X%)	XX (XX.X%)	XX (XX.X%)	XX (XX.X%)	XX (XX.X%)	XX (XX.X%)

TEAE = Treatment-Emergent Adverse Event.

Note: Percentages are calculated based on the number of subjects in the Safety population in each treatment group.

Note: Adverse events are classified as treatment-emergent if they started on or after the date of first dose of study treatment.

Adverse events with partial or missing start dates are classified as treatment-emergent, unless the non-missing components of the start date confirm otherwise.

Programming note: Use the Table 14.3.1.1 shell to produce

Table 14.3.1.1.1
Overview of number of subjects with TEAE during OLE Treatment Period
Safety Population (Japan)

Table 14.3.1.2.1
Treatment-Emergent Adverse Events by MedDRA System Organ Class and Preferred Term
Safety Population

MedDRA System Organ Class and Preferred Term	Gp1 (N=xx)	Gp 2 (N=xx)	Gp3 (N=xx)	Gp 4 (N=xx)	Gp5 (N=xx)	ZX008 OL (N=xx)	De Novo Subjects (N=xx)
Subjects with any TEAE	XX (XX.X%)	XX (XX.X%)	XX (XX.X%)	XX (XX.X%)	XX (XX.X%)	XX (XX.X%)	XX (XX.X%)
System Organ Class 1	XX (XX.X%)	XX (XX.X%)	XX (XX.X%)	XX (XX.X%)	XX (XX.X%)	XX (XX.X%)	XX (XX.X%)
Preferred Term 1	XX (XX.X%)	XX (XX.X%)	XX (XX.X%)	XX (XX.X%)	XX (XX.X%)	XX (XX.X%)	XX (XX.X%)
Preferred Term 2	XX (XX.X%)	XX (XX.X%)	XX (XX.X%)	XX (XX.X%)	XX (XX.X%)	XX (XX.X%)	XX (XX.X%)

TEAE = Treatment-Emergent Adverse Event.

Note: Percentages are calculated based on the number of subjects in the Safety population.

Note: Adverse events are classified as treatment-emergent if they started on or after the date of first dose of study treatment. Adverse events with partial or missing start dates are classified as treatment-emergent, unless the non-missing components of the start date confirm otherwise.

Note: A subject with more than one TEAE with the same preferred term is counted once for that term. A subject with more than one TEAE under a system organ class is counted once for that class.

Programming note: Use the Table 14.3.1.2.1 shell to produce same shell for 14.3.1.2.1.3 (Japan).

Table 14.3.1.2.1.3

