Safety Population (Japan)

Programming Note: use shell from Table 14.3.1.1 to produce the following tables.

Table 14.3.1.7
Overview of number of subjects with Treatment-Emergent Adverse Events of Special Interest
Safety Population

Table 14.3.1.7.1
Overview of number of subjects with Treatment-Emergent Adverse Events of Special Interest
Safety Population (Japan)

Add footnote: AESI=Adverse event of special interest.

Programming Note: use shell from Table 14.3.1.2.1 for

Table 14.3.1.8
Treatment Emergent Adverse events of special interest (TE AESI) by MedDRA System Organ Class and Preferred Term
Safety Population

Table 14.3.1.8.1
Treatment Emergent Adverse events of special interest (TE AESI) by MedDRA System Organ Class and Preferred Term
Safety Population (Japan)

Please change footnote from TEAE to TE AESI= Treatment emergent adverse event of special interest.

Table 14.3.1.9.1

Non-treatment Emergent Adverse Events Starting between Visits 12 and 13 of the Feeder Study, by MedDRA System Organ Class, Preferred Term and Prior Treatment in Feeder Study Safety Population

MedDRA System Organ Class and Preferred Term	Gp1 (N=xx)	Gp 2 (N=xx)	Gp3 (N=xx)	Gp 4 (N=xx)	Gp5 (N=xx)	Gp 9 (N=xx)
Subjects with Any Non-TEAE Starting Between Visits 12 and 13 of Feeder Study	XX (XX.X%)	XX (XX.X%)	XX (XX.X%)	XX (XX.X%)	XX (XX.X%)	XX (XX.X%)
System Organ Class 1	XX (XX.X%)	XX (XX.X%)	XX (XX.X%)	XX (XX.X%)	XX (XX.X%)	XX (XX.X%)
Preferred Term 1	XX (XX.X%)	XX (XX.X%)	XX (XX.X%)	XX (XX.X%)	XX (XX.X%)	XX (XX.X%)
Preferred Term 2	XX (XX.X%)	XX (XX.X%)	XX (XX.X%)	XX (XX.X%)	XX (XX.X%)	XX (XX.X%)
.						
.						

TEAE = Treatment-Emergent Adverse Event.

Note: Percentages are calculated based on the number of subjects in the Safety population.

Note: Adverse events in this table have a start date preceding the start of treatment in Study 1503, hence were classified as “non-treatment-emergent”.

Adverse events are classified as treatment-emergent if they started on or after the date of first dose of study treatment. Adverse events with partial or missing start dates are classified as treatment-emergent, unless the non-missing components of the start date confirm otherwise.

Note: A subject with more than one non-TEAE with the same preferred term is counted once for that term. A subject with more than one Non-TEAE under a system organ class is counted once for that class.

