Programming Note: Include only events whose start date is between Day -30 (inclusive) and Day -1 (inclusive), counting study days from beginning of OLE Treatment period, not core. There will be no De Novo Column for this table.

Use the Table 14.3.1.9.1 shell for

Table 14.3.1.9.1.1

Non-treatment Emergent Adverse Events Starting between Visits 12 and 13 of the Feeder Study, by MedDRA System Organ Class, Preferred Term and Prior Treatment in Feeder Study Safety Population (Japan)

Table 14.3.1.9.2
TEAEs starting in the 1st month of OLE by System Organ Class, Preferred, Term and Prior Treatment in Feeder Study
Safety Population

MedDRA System Organ Class and Preferred Term	Gp1 (N=xx)	Gp 2 (N=xx)	Gp3 (N=xx)	Gp 4 (N=xx)	Gp5 (N=xx)	De Novo Subjects (N=xx)
Subjects with any TEAE starting in the first month.	XX (XX.X%)	XX (XX.X%)	XX (XX.X%)	XX (XX.X%)	XX (XX.X%)	XX (XX.X%)
System Organ Class 1	XX (XX.X%)	XX (XX.X%)	XX (XX.X%)	XX (XX.X%)	XX (XX.X%)	XX (XX.X%)
Preferred Term 1	XX (XX.X%)	XX (XX.X%)	XX (XX.X%)	XX (XX.X%)	XX (XX.X%)	XX (XX.X%)
Preferred Term 2	XX (XX.X%)	XX (XX.X%)	XX (XX.X%)	XX (XX.X%)	XX (XX.X%)	XX (XX.X%)

TEAE = Treatment-Emergent Adverse Event.

Note: A subject with more than one TEAE with the same preferred term is counted once for that term. A subject with more than one TEAE under a system organ class is counted once for that class.

Programming note:

Include only events starting on or after Day 1 up to Day 30 (counting from beginning of OLE Treatment period, NOT Core).

Use same Table 14.3.1.9.2 shell for

Table 14.3.1.9.2.1
TEAEs starting in the 1st month of OLE by System Organ Class, Preferred, Term and Prior Treatment in Feeder Study
Safety Population (Japan)

Programing note: Use the 14.3.1.9.1 shell to produce the following tables. Include only events starting on or after Study Day31 up to Day 60 (counting from beginning of OLE Treatment period, NOT Core)

Table 14.3.1.9.3
TEAEs starting in the 2nd month of OLE by System Organ Class, Preferred Term and Prior Treatment in Feeder Study
Safety Population

Table 14.3.1.9.3.1
TEAEs starting in the 2nd month of OLE by System Organ Class, Preferred Term and Prior Treatment in Feeder Study
Safety Population (Japan)

Programing note: Use the Table 14.3.1.9.1 shell for the following tables. Include only events starting on or after Study Day61 up to day 90(counting from beginning of OLE Treatment period, NOT Core)

Table 14.3.1.9.4

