Note: A subject with more than one TEAE with the same preferred term is counted once for that term. A subject with more than one TEAE under a system organ class is counted once for that class.

Programming note: Use shell for 14.3.1.10.1 for 14.3.1.10.1.1

Table 14.3.1.10.1.1
 Treatment-Emergent Adverse Events that Occurred in at least 5% of Subjects during Double-blind Treatment Period by MedDRA System Organ Class and Preferred Term
 with Mean Time to Onset (days) and Mean Duration (days)
 Safety Population (Japan)

Table 14.3.1.10.2
 Treatment-Emergent Adverse Events that Occurred in at least 5% of Subjects during Double-blind through Open-label Treatment Periods by MedDRA System Organ Class and Preferred Term, Mean Average Dose in ZX008-1503 with Mean Time to Onset (days) and Mean Duration (days)
 Safety Population

MedDRA System Organ Class and Preferred Term	ZX008 0 - < 0.2 mg/kg [1] (N=xx) n (%) / Mean Onset/ Mean Duration	ZX008 0.2 - < 0.4 mg/kg (N=xx) n (%) / Mean Onset/ Mean Duration	ZX008 0.4 - < 0.6 mg/kg (N=xx) n (%) / Mean Onset/ Mean Duration	ZX008 0.6 - < 0.8 mg/kg (N=xx) n (%) / Mean Onset/ Mean Duration	Any OLE ZX008 (N=xx) n (%) / Mean Onset/ Mean Duration
	Subjects with any TEAE starting in the first month.	XX (XX.X%) / xx.x /xx.x	XX (XX.X%) / xx.x /xx.x	XX (XX.X%) / xx.x /xx.x	XX (XX.X%) / xx.x /xx.x
System Organ Class 1	XX (XX.X%) / xx.x /xx.x	XX (XX.X%) / xx.x /xx.x	XX (XX.X%) / xx.x /xx.x	XX (XX.X%) / xx.x /xx.x	XX (XX.X%) / xx.x /xx.x
Preferred Term 1	XX (XX.X%) / xx.x /xx.x	XX (XX.X%) / xx.x /xx.x	XX (XX.X%) / xx.x /xx.x	XX (XX.X%) / xx.x /xx.x	XX (XX.X%) / xx.x /xx.x
Preferred Term 2	XX (XX.X%) / xx.x /xx.x	XX (XX.X%) / xx.x /xx.x	XX (XX.X%) / xx.x /xx.x	XX (XX.X%) / xx.x /xx.x	XX (XX.X%) / xx.x /xx.x

TEAE = Treatment-Emergent Adverse Event.

Note: Percentages are calculated based on the number of subjects in each treatment group.

Note: Mean Onset and Mean Duration are measured in days. The onset day is the study day at the adverse event onset. The duration is the number of days from onset to resolution or from onset to last follow-up day if the event was ongoing.

Note: Adverse events are classified as treatment-emergent if they started on or after the date of first dose of study treatment. Adverse events with partial or missing start dates are classified as treatment-emergent, unless the non-missing components of the start date confirm otherwise.

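### Treatment emergence rests on AE start date alone, so a core-study event that worsens in the extension can drop out of the main OLE TEAE summaries

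*SAP*

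**What the plan says.** Four places in the SAP bear on this.

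- **Section 6.4.1, core-study events.** "AEs from the core studies will be considered medical history unless there is an increase in the frequency or severity of the condition". A core event that gets worse is thus meant to count as an AE of the extension.
- **Section 6.4.1, TEAE definition, which follows directly.** "A TEAE is defined as any AE that based on start date information occurs after the first intake of study treatment". Worsening is not mentioned.
- **Section 6.2.7.** Core AEs that ended before 1503 began become medical history. For the rest: "Ongoing AEs will be included as such in 1503". No start-date convention is given.
- **Appendix 1 shells.** The footnote to the TEAE tables reads: "Adverse events are classified as treatment-emergent if they started on or after the date of first dose of study treatment". The footnote to Table 14.3.1.9.1 shows which first dose is meant: "Adverse events in this table have a start date preceding the start of treatment in Study 1503, hence were classified as" non-treatment-emergent.

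**The concern.** The primary objective (Section 2.1) is long-term safety and tolerability. Under Section 3.2, subjects from the double-blind studies have moved to 0.2 mg/kg in the transition period before they enter, and the dose may then be raised during the OLE. An event that begins before OLE Day 1 and worsens after it is therefore a foreseeable pattern. Suppose decreased appetite starts as mild in the core study and becomes severe in OLE Month 4. Under a pure start-date rule it is the same event with a core start date, and the main OLE summaries would show neither the event nor its severe grade.

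The SAP leans the other way when dates are missing. Section 6.1.7.2 imputes so that an AE that might have begun after first dosing is handled as a TEAE. Leaving out a known worsening does not fit that intention.

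**Working it through.** No arithmetic applies, because this is a classification rule. Setting the rules side by side for a core-study AE:

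| Status of the core AE | Section 6.2.7 | Section 6.4.1, history rule | TEAE rule (6.4.1 and shells) |
|---|---|---|---|
| Ended before 1503 | Medical history | Medical history | Not a TEAE |
| Ongoing at entry, unchanged | AE in 1503 | Medical history | Not a TEAE |
| Ongoing at entry, worse in the OLE | AE in 1503 | AE in 1503 | Depends on the start date used |

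The second row is a direct conflict: Section 6.2.7 asks whether the event has ended, while Section 6.4.1 asks whether it has worsened. The third row is the one at issue, and it has two possible outcomes.

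1. *Same record, core start date kept.* The event is not a TEAE. It is absent from Tables 14.3.1.1 (overview), 14.3.1.2.1 (system organ class and preferred term), 14.3.1.2.1.2 (decreased appetite), 14.3.1.4 (serious), 14.3.1.5.1 (related) and 14.3.1.6 (maximum severity). It is also absent from 14.3.1.3, whose shell is titled for TEAEs leading to discontinuation although Section 6.4.1.2 plans that summary for all AEs.
2. *Worsening entered as a new event with its own start date.* The event is a TEAE and appears in those tables wherever it meets their other criteria.

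The SAP does not choose between these. The natural reading of Section 6.2.7 is the first, and two programmers could produce different tables from the same data.

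Under outcome 1, the remaining outputs recover the following:

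- **Table 14.3.1.9.1**, the one summary of non-treatment-emergent events, takes only starts from Day -30 to Day -1. Core treatment ran for 14 weeks, and the Cohort 1 transition for up to 24, so earlier starts fall outside it. It does not show later worsening.
- **Table 14.3.1.10.1** counts double-blind onsets but cuts event duration at the end of the double-blind study.
- **Table 14.3.1.10.2** is titled "Treatment-Emergent Adverse Events that Occurred in at least 5% of Subjects during Double-blind through Open-label Treatment Periods". It can include a core onset on ZX008 if the term reaches 5%. It has no severity breakdown and takes onset and duration from the earliest occurrence, so the OLE worsening is not visible.
- **Listings** of all AEs, SAEs and discontinuations would contain the event, but they give no rates.

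**The case against.** The strongest reply is that the SAP already intends worsened core events to count, and that the convention for recording a worsening is commonly set in the protocol or the CRF instructions. If sites enter a worsening as a new event, the start-date rule makes it a TEAE and nothing is lost. That is possible and cannot be ruled out from the SAP. It does not remove the problem: the definition and its shell footnotes still omit the criterion that Section 6.4.1 itself uses, and Section 6.2.7 points to the old record being carried forward.

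A reader might infer that such events never reach any TEAE table or go unreported. The document does not support that. Table 14.3.1.10.2 can count them at first onset, Section 6.4.1.2 plans listings of all AEs and serious AEs, and its text on discontinuation covers all AEs. For the appetite example there is also a partial safety net: Section 6.4.5 summarises weight loss of at least 5%, 7% and 10% from OLE baseline whatever the AE start date.

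A reader might also infer that all subjects given active drug in the core studies are exposed to worsening at doses above their core dose. By Table 1 they number 218 of 338 (64%), but that is a measure of core exposure, not a rate of worsening. For Groups 3 and 4 (80 + 40 = 120 of those 218, or 55%) the OLE maximum in Section 3.2 equals the core dose, so within those limits they can rise only from the transition dose back towards it.

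**Conclusion.** The point holds as an internal conflict with a one-directional consequence. The SAP uses worsening to decide what is an AE of the extension, then leaves it out when deciding what is treatment-emergent. As written, the main OLE TEAE summaries can understate both incidence and maximum severity for events ongoing at entry. This rests on one assumption that the SAP neither states nor excludes: that a carried-in event keeps its core start date.

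No subject count can be given. It would need the share of subjects entering with an ongoing AE and the share of those who worsen, and the document gives neither. The loss concerns the summary tables, not the listings. It should still be corrected, because those summaries are the main evidence on the primary objective.

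**What to change.** In Section 6.4.1, define a TEAE as an AE that starts on or after the first dose in Study 1503, or that was present before it and increases in severity or frequency on or after that date. Count the second kind at the worsened severity, with the date of worsening as onset.

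Then align the rest:

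- Give Sections 6.2.7 and 6.4.1 one rule for core AEs ongoing at entry, including how a worsening is recorded and dated.
- Change the TEAE shell footnotes to the new definition. Settle whether an event on the day of first dose counts: Section 6.4.1 takes events after first intake, while the shells also include that day.
- Make the shell for Table 14.3.1.3 cover all AEs leading to discontinuation, as Section 6.4.1.2 plans.

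The cost is SAP wording and one derivation flag. TEAE counts will be slightly higher, and a footnote should explain any difference from earlier outputs produced under the start-date rule.

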6.4.1.2 Treatment Emergent Adverse Events

The following summaries will display the number and percentage of subjects with an adverse event as well as the corresponding number of events by system organ class (SOC) and preferred term (sorted alphabetically):

- All TEAEs
- All TEAEs occurring in $\geq 5\%$ of subjects
- Serious TEAEs
- TEAEs by Maximum Severity
- TEAEs by prior treatment group, with onset before or up to Visit 1, Visit 2; Visit 3; Visit 4
- Study Drug Related TEAEs

- Study Drug Related TEAEs occurring in $\geq 5\%$ of subjects
- All AEs that lead to premature discontinuation from the study

No inferential statistical methods (i.e., methods that yield p-values) will be used to compare treatment groups on the frequency or severity of AEs.

These summaries will be provided for the OLE treatment period.

Additionally, the following listings will be produced for all enrolled subjects:

- All AEs, events considered to be TEAE will be identified in the listing
- Serious AEs
- AEs that lead to premature discontinuation from the study

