Programming notes: If subjects has multiple events with the same preferred term, count the worst case (if one event is unresolved, count the unresolved one).

Programming Note: Use the same shell for 14.3.1.2.1.5 (Japan).

Programming Note: Use the shell for Table 14.3.1.2.1) for the following Tables:

Table 14.3.1.2.2
Treatment-Emergent Adverse Events occurring in at least 5% of the subjects by MedDRA System Organ Class and PT
Safety Population

For the interim: Since we are only tabulating for “All subjects”,
Add the footnote: “Events listed are those for which the % of subjects having that AE is $\geq 5.0\%$ of subjects.”

Table 14.3.1.3
TEAEs leading to study discontinuation by MedDRA System Organ Class and Preferred Term
Safety Population

Table 14.3.1.3.1
TEAEs leading to study discontinuation by MedDRA System Organ Class and Preferred Term
Safety Population (Japan)

Table 14.3.1.4
Serious TEAEs by MedDRA System Organ Class and Preferred Term
Safety Population

Table 14.3.1.4.1
Serious TEAEs by MedDRA System Organ Class and Preferred Term
Safety Population (Japan)

Table 14.3.1.5.1
Related TEAEs MedDRA System Organ Class and Preferred Term
Safety Population

Table 14.3.1.5.2
Related TEAEs occurring in at least 5% of subjects by MedDRA System Organ Class and Preferred Term
Safety population

Table 14.3.1.5.3
Related TEAEs MedDRA System Organ Class and Preferred Term
Safety Population (Japan)

Table 14.3.1.5.4
Related TEAEs occurring in at least 5% of subjects by MedDRA System Organ Class and Preferred Term
Safety population (Japan)

TLF Shells

Zogenix International Limited
ZX008-1503

For the interim: Since we are only tabulating for "All subjects",
Add the footnote: "Events listed are those for which the % of subjects having that AE is $\geq 5.0\%$ of subjects."

PUBLIC COPY
This document cannot be used to support any marketing authorization application and any extensions or variations thereof.

Table 14.3.1.6
 TEAEs by Maximum Severity, MedDRA System Organ Class and Preferred Term
 Safety Population

MedDRA System Organ Class and Preferred Term	Maximum Severity	Gp1 (N=xx)	Gp 2 (N=xx)	Gp3 (N=xx)	Gp 4 (N=xx)	Gp5 (N=xx)	Gp 9 (N=xx)	De Novo Subjects (N=xx)
Subjects with any TEAE	Mild	XX (XX.X%)	XX (XX.X%)	XX (XX.X%)	XX (XX.X%)	XX (XX.X%)	XX (XX.X%)	XX (XX.X%)
	Moderate	XX (XX.X%)	XX (XX.X%)	XX (XX.X%)	XX (XX.X%)	XX (XX.X%)	XX (XX.X%)	XX (XX.X%)
	Severe	XX (XX.X%)	XX (XX.X%)	XX (XX.X%)	XX (XX.X%)	XX (XX.X%)	XX (XX.X%)	XX (XX.X%)

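### The adverse-event shells omit the event counts that Section 6.4.1.2 requires, and the overview shell does not match the list in Section 6.4.1.1

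*SAP*

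**What the plan says.** **Text, event counts.** SAP Section 6.4.1.2 introduces eight summaries: all TEAEs, TEAEs in at least 5% of subjects, serious TEAEs, TEAEs by maximum severity, TEAEs by prior treatment group and early onset, related TEAEs, related TEAEs in at least 5%, and AEs leading to discontinuation. For these it says "The following summaries will display the number and percentage of subjects with an adverse event as well as the corresponding number of events", broken down by system organ class and preferred term.

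**Text, overview.** Section 6.4.1.1 is different. It asks for subjects only: "The number and percent of patients with at least one of the following events will be summarized in an overall summary table". Its seven items are any TEAE, serious, related, related serious, severe, AESI and deaths, for the OLE treatment period.

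**Shells.** The shell for Table 14.3.1.2.1 has cells for a number and a percentage only, and its footnote reads "A subject with more than one TEAE with the same preferred term is counted once for that term". A programming note extends that layout to other tables: "Use the shell for Table 14.3.1.2.1) for the following Tables". The overview shell, Table 14.3.1.1, includes a row "At Least one Fatal TEAE" and ends with "At Least one TEAE Leading to Discontinuation of Study Treatment". The notes ahead of the table list in the shells document say that the shells are meant for the final study report.

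**The concern.** Long-term safety and tolerability is the primary objective (Section 2.1), and treatment runs for up to 36 months. A subject-once percentage records whether a subject ever had an event. The event count is the only statistic in Section 6.4.1.2 that reflects how often events come back. If programming follows the shells, as it normally does, the final report departs from the SAP text on the primary objective. Section 6.10 records no change that would explain the departure.

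The overview has a smaller problem. A reader who goes to that one table for the headline safety figures will not find two of the promised items, and will find a near-substitute for a third.

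**Working it through.** The SAP gives no figure to reproduce here. The check is text against shell, followed by an illustration of size.

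**1. Event counts: Section 6.4.1.2 against the shells**

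| Summary in 6.4.1.2 | Shell | Event count? |
|---|---|---|
| All TEAEs | 14.3.1.2.1 | No |
| TEAEs in at least 5% | 14.3.1.2.2 (reuses 14.3.1.2.1) | No |
| Serious TEAEs | 14.3.1.4 (reuses 14.3.1.2.1) | No |
| Maximum severity | 14.3.1.6, subject counted once at worst grade | No |
| By prior treatment and early onset | 14.3.1.9.2 to 14.3.1.9.4 | No |
| Related TEAEs | 14.3.1.5.1 (reuses 14.3.1.2.1) | No |
| Related, at least 5% | 14.3.1.5.2 (reuses 14.3.1.2.1) | No |
| Leading to discontinuation | 14.3.1.3 (reuses 14.3.1.2.1) | No |

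Result: 0 of 8. The onset-and-duration Tables 14.3.1.10.1 and 14.3.1.10.2 do not fill the gap, because for a subject with repeats they use only the earliest occurrence.

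**2. Overview: Section 6.4.1.1 against shell 14.3.1.1**

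| Item in 6.4.1.1 | Row in 14.3.1.1 | Found elsewhere |
|---|---|---|
| Any TEAE | Yes | |
| Serious | Yes | |
| Related | Yes | |
| Related serious | Yes | |
| Severe | No | 14.3.1.6, severe line under any TEAE |
| AESI | No | 14.3.1.7 and 14.3.1.8 |
| Deaths | As fatal TEAE | Deaths listed in 14.3.2.1 |

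Four items match, one is approximated and two are absent. The shell adds one row that the text does not list, for discontinuation.

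**3. Deaths against fatal TEAEs.** Under Section 6.4.1 a TEAE starts after the first intake of study treatment. Section 6.2.7 carries AEs still ongoing from the core study into this study. A carried-over event that proves fatal during the OLE is a death but, going by its start date, not a fatal TEAE.

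**4. What a subject percentage can hide.** The SAP gives no AE rates, so those below are assumptions. For a constant rate *r* per year over 3 years, mean events per subject are 3*r*. The proportion with at least one event is 1 − exp(−3*r*) under Poisson. With strong between-subject variation (gamma-Poisson, shape 1) it is 3*r*/(1 + 3*r*).

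| Rate per year | Mean events | Poisson | Gamma-Poisson |
|---|---|---|---|
| 0.1 | 0.3 | 1 − exp(−0.3) = 25.9% | 0.3/1.3 = 23.1% |
| 0.2 | 0.6 | 1 − exp(−0.6) = 45.1% | 0.6/1.6 = 37.5% |
| 1 | 3 | 1 − exp(−3) = 95.0% | 3/4 = 75.0% |
| 2 | 6 | 1 − exp(−6) = 99.8% | 6/7 = 85.7% |

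Events double in both pairs. The percentage shows most of that for the less frequent event and little of it for the frequent one. In the 30-day windows of Tables 14.3.1.9.2 to 14.3.1.9.4 saturation is not an issue even at the high rates: 1 − exp(−30/365.25) = 7.9% and 1 − exp(−60/365.25) = 15.1%. Those tables cover only the first three months.

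**The case against.** The best reply is that very little information is missing.

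- **Severe TEAEs and AESIs.** A reader might infer that these counts are lost. They are not. Counted at maximum severity, the severe line under any TEAE in Table 14.3.1.6 is exactly the number of subjects with at least one severe TEAE. Table 14.3.1.7 is a dedicated AESI overview, and Table 14.3.1.8 breaks AESIs down by class and term. This stands: the overview gap is one of placement.
- **Deaths.** A reader might infer that deaths go unreported. The documents do not support that: there is a fatal-TEAE row, and Table 14.3.2.1 lists deaths. Table 6 also treats AEs up to 30 days after the last dose as treatment-emergent, and Section 6.4.1 allows a core-study AE that increases in severity to count as more than medical history. Within the OLE scope the two labels can differ essentially only for a fatal event that began before the first OLE dose.
- **Repeated events.** A reader might infer that recurrence is shown nowhere. Listing 16.2.7.1 gives individual events with start and stop dates. Table 14.2.9.1 tabulates the number of unique status epilepticus events, and Table 14.2.8.1 gives seizure admissions per 100 subject-years. This also stands, but a listing does not replace the tabulated counts by class and term that Section 6.4.1.2 promises.
- **Scope.** Event counts are not required everywhere. Section 6.4.1.1 asks only for subjects, and Section 6.4.2 asks for no event count for AESIs.
- **Saturation.** It depends on the rate, and at low rates the subject percentage remains informative. A raw event count is also not a rate when follow-up varies.

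None of this removes the direct mismatch between Section 6.4.1.2 and its shells.

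**Conclusion.** The point holds as a contradiction between text and shells. All eight summaries in Section 6.4.1.2 are specified with event counts, and no corresponding final-report shell has one, so recurrence by class and preferred term is left to listings. The overview shell lacks two of the seven items in Section 6.4.1.1 and relabels a third.

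No estimate is biased, and no required subject count for severe TEAEs or AESIs is lost. The practical loss is greatest for frequent, recurring events and small for rare ones; its size here rests on assumed rates, a constant hazard and a full three years of follow-up. It should be corrected because safety is the primary objective and the SAP already commits to the statistic.

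**What to change.** 1. Add an event-count column beside the number and percentage in shell 14.3.1.2.1, and so in 14.3.1.2.2, 14.3.1.3, 14.3.1.4, 14.3.1.5.1 and 14.3.1.5.2. Do the same in 14.3.1.6 and in 14.3.1.9.2 to 14.3.1.9.4. The month 2 and month 3 tables are told to reuse shell 14.3.1.9.1, so that instruction must be updated too. Carry the change into the Japan copies. For AESI Table 14.3.1.8 an event count is optional.
2. Add rows to shell 14.3.1.1, and to its Japan copy, for subjects with at least one severe TEAE and at least one AESI. Table 14.3.1.7 reuses this shell, so suppress the AESI row there.
3. Add a deaths row for the OLE treatment period beside the fatal-TEAE row, keeping both. Deaths outside that period would go beyond Section 6.4.1.1 and should be labelled as an addition if wanted.

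The cost is a shell edit, a count from the existing AE dataset and slightly wider tables. No new data are needed.
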